1.2.2 Secondary Objectives

1. Measure the correlation between blood / CSF levels of inflammatory biomarkers (e.g. hsCRP, IL-6) and cognitive function (MoCA).
2. Demonstrate a reduction in blood / CSF levels of inflammatory biomarkers (e.g. hsCRP, IL-6) in the LDIVH treated subjects compared to controls.
3. Demonstrate a reduction in cerebral vasospasm in the LDIVH treated subjects compared to controls by measuring the proportion of patients in each group who:
 - i. Demonstrate moderately severe or severe angiographic vasospasm by CTA or DSA obtained within the prime vasospasm window
 - ii. Demonstrate moderately severe or severe vasospasm on transcranial Dopplers (TCDs)
 - iii. Demonstrate vasospasm related CT infarctions
4. Demonstrate a reduction in “Delayed Cerebral Ischemia” as defined by the Neurocritical Care Society:
 - i. Symptoms of neurological deterioration (e.g., hemiparesis, aphasia, altered consciousness) presumed to be related to ischemia
 - ii. Symptoms persist for more than one hour
 - iii. Symptoms cannot be explained by other physiological abnormalities
5. Demonstrate a reduction in the need for “rescue therapy” for delayed cerebral ischemia and / or symptomatic cerebral vasospasm
6. Demonstrate a difference between the LDIVH treated subjects and controls in the proportion of patients in each group who:
 - i. Have any fever (Temperature $\geq 38.3^{\circ}\text{C}$ / 101.0°F)
 - ii. Have multiple fevers (≥ 3 fever episodes)
7. Demonstrate a significant difference in “fever burden” between LDIVH treated subjects and control subjects
8. Demonstrate a difference between LDIVH treated subjects and controls in mean Daily Fever Burden during the LDIVH infusion.

9. Demonstrate better clinical outcomes in the LDIVH treated subjects compared to controls with one of the following measures:
 - i. mRS at 90 days and 1-year (Ordinal Regression Analysis)
 - ii. Barthel Index at 90 days
 - iii. Center for Epidemiologic Studies Depression Scale (CES-D) at 90 days and 1-year
 - iv. QOLIBRI-OS at 90 days and 1-year
 - v. Lawton IADLs at 90 days
 - vi. Trail Making Test Parts A&B at 90 days
 - vii. Return to Work Status at 90 days and 1-year
 - viii. MoCA at 1-year
10. Perform Pre-specified Subgroup Analysis of Outcome measures for LDVIH and Control groups using the following subgroup designations:
 - i. Sex (Male versus Female)
 - ii. Admission CT Hijdra Sum Score (<23 versus ≥ 23)

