 - iii. Aneurysm location (ACoA Aneurysm location vs. all others; any location; anterior circulation versus posterior circulation)
 - iv. Infection requiring Antibiotic Treatment versus no infection
 - v. Elevated hsCRP at enrollment vs. normal levels at enrollment
 - vi. WFNS 1 vs. 2
 - vii. Modified Fisher grade 3 and 4 while excluding accidental enrollments with Modified Fisher not equal to 3 or 4
 - viii. Chemical DVT prophylaxis: UFH 5000 units twice daily, or increased dose in obese patients according to SOC
 - ix. LDVIH arm: LDIVH infusion >10 days vs. ≤ 10 days
 - x. LDIVH arm: Initiation of LDIVH within 48 hours of hemorrhage ictus vs. > 48 hours
 - xi. LDIVH arm: Anti-Xa (Infusion Day 6) value < 0.20 IU/mL vs. ≥ 0.20 IU/mL
 - xii. Vasospasm related CT infarction vs. No vasospasm related CT infarction
 - xiii. Tobacco smoking versus no tobacco smoking

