10. DATA ANALYSIS AND CONSIDERATIONS

10.1 Sample Size Justification and Primary Clinical Effect Analysis

The sample sizes justification is based on the combination of the pilot data that we have previously observed ([name] Unpublished) and results based on Schweizer et al. (2012). Two main outcomes, MoCA and MMSE, were compared by Schweizer et al (2012) and their validity was compared. The two measures have slightly different cut-offs for defining impairments (MoCA score <26 and MMSE score <27). In this study we will use MoCA as a primary outcome measure. Based on published data, MoCA has mean (SD) of 25.4 (2.8) with n=32. In our pilot data with small sample sizes, we observed an overall mean of 24.6 (5.4) with n=47. The separate group means were 26.4 (2.3) with n=25 and 22.7 (7.0) with n=22 in the treatment and control arms, respectively. Because the two groups were heterogeneous, we assume SD=2.5 in treatment group and SD=7.0 in control group. As hypothesized and as documented in the preliminary data, MoCA is higher in the treatment arm than in the control arm, and so we will use one-sided test procedures. The study design is that of a two group, multicenter randomized clinical trial.

Table S1: Sample sizes based on having alpha=5% and SD1=7.0 and SD2=2.5 to detect 3 unit (effect size=0.5 SD) using one-sided two-sample t test with unequal variances.

Power	N1	Total N
80%	40	80
85%	46	92
90%	54	108

Given the number of centers participating, we plan to enroll 40 evaluable subjects in each arm. Assuming 8 centers, a sample size of 80 would be realized by recruiting 10 per center. Note that we need to balance the number of treatment and controls to be equal at each center, but not necessarily having equal number of subjects at each center. However, the numbers in the tables do not adjust for loss to follow up, drop outs, the ability to adjust for covariates, or for the loss of degrees of freedom for the centers in a test or model. The discussion below addresses further aspects of the sample size consideration.

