Based on a desired total of 40 patients per arm, and an assumed dropout rate of 10%, the trial would require 44 patients in each arm for a total enrollment plan of 88 patients distributed over 8 sites, or on average 11 patients per site. There are multiple covariates that may confound the findings and this needs to be addressed in the design of the study. The primary factors are: center, risk associated with anterior communicating artery (ACoA) aneurysm location (1 versus others), age (≤ 70 versus > 70) and sex. The other factors are: fever (yes, no), transfusion (yes, no), vasospasm (yes, no). Due to limited resources only primary factors (ACoA, group and sex) will be considered to balance the allocation of treatment and control in 1:1 ratio. Thus, the randomization will be balanced within each of 6 strata. Advanced age will be controlled for by eliminating enrollment for patients over 70 years. Effect of the remaining factors will be addressed in the multi-variate model.

We will also compare the frequency of severe cognitive impairment (MoCA ≤ 20) in the two arms. Previous data demonstrated a rate of 0% (0/25) severe cognitive impairment in the heparin treatment group and approximately 32% (7/22) in the control group. In our currently planned study, we will assume a 5% rate of severe cognitive impairment in the heparin treatment group and a 32% rate of severe cognitive impairment in the control group. This will also allow a demonstration of power = 80% with alpha at 0.05 for our previously calculated sample sizes ($n_1=40$ and $n_2=40$) using a two-sample one-sided binomial test. This binomial calculation provides a second sample size estimate that supports our previous estimate of needing 40 patients per group. Therefore the final sample size estimation will be placed at a total of 88 patients to account for a 10% dropout rate leaving a final number of patients available for primary outcome analysis of 80 patients. Drop-out will be monitored during the enrollment process. If we approach 8 patients lost to follow-up then additional enrollments (beyond 88) will be considered if funding is available.

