10.2 Correlation Analysis

In addition to testing the correlations with one sample (treatment + control groups together), we can identify an absolute correlation of 0.27 from no correlation at the same design parameters. When comparing within each treatment group the detectable correlation will be at least 0.37. For comparing correlations between two groups (treatment and controls), the difference of detectable correlation is at least 0.50 at the same design parameters. In all three types of effect size calculations, the detectable effect sizes are moderate-to- large (Cohen, 1988). Note that sample size justification does not take into account the multiple but correlated outcomes within same subjects. Sample size calculation is based on methods described in Chow et al (2008) and Cohen (1988).

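### Three measured quantities (Hijdra score, enrollment hsCRP, day-6 anti-Xa) are prespecified only as two-level subgroups, which gives up about a third or more of the information in an already small trial

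*Protocol*

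**What the plan says.** Protocol section 1.2.2, item 10, lists prespecified subgroups for comparing outcome measures. Three of them cut a continuous or many-level measure in two:

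- Subgroup ii: "Admission CT Hijdra Sum Score", below 23 against 23 or more.
- Subgroup v: "Elevated hsCRP at enrollment vs. normal levels at enrollment". No threshold is given, and sections 3 and 6.11 have hsCRP run by each site's own clinical laboratory.
- Subgroup xi: "LDIVH arm: Anti-Xa (Infusion Day 6) value", below 0.20 against 0.20 IU/mL or more, in the LDIVH arm only.

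No reason is stated beside any of the cuts. Elsewhere the protocol leaves such measures uncut: the synopsis describes the correlation of MoCA with inflammatory biomarkers on levels, with and without adjustment for the Hijdra score. Section 10.2 gives detectable correlations for that kind of analysis: 0.27 with both arms together and, for one arm, "When comparing within each treatment group the detectable correlation will be at least 0.37". It gives no detectable effect or power for the subgroups.

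**The concern.** The synopsis says the trial is meant to inform whether a Phase III study is warranted. Three questions bear on that: whether cognition improves with heparin exposure, whether benefit depends on how much blood was seen on CT, and whether it depends on inflammation at entry. With about 40 evaluable patients per arm, each is hard to answer even with all the data used. A two-level cut treats everyone on one side as alike and places two patients just either side of the line in opposite groups.

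For hsCRP there is a further difficulty. With no threshold and local laboratories, who counts as elevated could depend on the site's reference limit. For anti-Xa, section 5.2 prefers the upper end of the 0.1–0.3 IU/mL target, so an even split at 0.20 cannot be taken for granted.

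**Working it through.** **Inputs from the protocol**
- Alpha 5%: "Table S1: Sample sizes based on having alpha=5% and SD1=7.0 and SD2=2.5 to detect 3 unit" (section 10.1).
- Sidedness: "and so we will use one-sided test procedures" (section 10.1).
- Power 80%: "This will also allow a demonstration of power = 80% with alpha at 0.05" (section 10.1).
- Sample size: "we plan to enroll 40 evaluable subjects in each arm" (section 10.1), with 44 per arm enrolled.
- Benchmark correlations 0.27 and 0.37 (section 10.2).

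**Inputs assumed**
- The predictor is normally distributed.
- The share of patients on each side of a cut is not given for any of the three measures, so a range is shown.

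**Step 1. Reproduce the plan's figures.** The t test for a correlation has noncentrality r/√(1−r²) × √n on n−2 degrees of freedom. Solving for r at 80% power and one-sided 5% gives 0.270 at n = 80 and 0.372 at n = 40. These match the stated 0.27 and 0.37. Two-sided, the answers would be 0.302 and 0.414, so the stated values are one-sided.

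**Step 2. Effect of a cut on the correlation.** Cutting a normal predictor at quantile q multiplies r by φ(z_q)/√(q(1−q)). The square of that factor is the share of information kept.

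| Split | Factor | Information kept | 0.37 becomes |
|---|---|---|---|
| 50/50 | 0.798 | 64% | 0.295 |
| 30/70 | 0.759 | 58% | 0.281 |
| 20/80 | 0.700 | 49% | 0.259 |
| 10/90 | 0.585 | 34% | 0.216 |

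**Step 3. Power for a within-arm association of 0.37 (the anti-Xa question).** Fisher z: power = Φ(√(n−3) × atanh(r) − 1.645).
- n = 40, continuous: √37 × atanh(0.37) − 1.645 = 6.083 × 0.388 − 1.645 = 0.72, power 76%.
- n = 40, median split: 6.083 × atanh(0.295) − 1.645 = 6.083 × 0.304 − 1.645 = 0.21, power 58%.
- n = 44, continuous: 6.403 × 0.388 − 1.645 = 0.84, power 80%.
- n = 44, median split: 6.403 × 0.304 − 1.645 = 0.30, power 62%.

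Uneven splits at n = 40 give 54% (30/70), 49% (20/80) and 38% (10/90). At n = 44 they give 58%, 52% and 41%. A simulation at n = 40 gave 77% continuous and 60% with a median split. Fisher z is slightly more cautious than the method in step 1, which is why it shows 76% rather than 80% at n = 40. The loss is about 18 points either way.

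**Step 4. Hijdra and hsCRP.** Here the question is whether the treatment effect changes with the covariate. The protocol assumes no interaction size, so the figures below are illustrations only. They come from simulated trials with 40 per arm, SDs 7.0 and 2.5, a normal covariate, heteroscedasticity-robust (HC3) standard errors and a two-sided 5% test.

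| Change in treatment effect per covariate SD (MoCA points, assumed) | Continuous | Median cut |
|---|---|---|
| 1 | 12–13% | 9% |
| 1.5 | 23% | 16% |
| 2 | 34–37% | 24–25% |
| 3 | 66–67% | 47–50% |

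The last row is extreme: an interaction of 3 points per SD equals the whole planned treatment effect of 3 points. At smaller sizes the continuous test is better, but both are weak.

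**The case against.** The case against is substantial, and part of it stands.

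- A reader might infer that the cuts take 18 points off the plan's own detectable correlation. They do not. The 0.37 belongs to the MoCA–biomarker correlation, which is described without cuts and keeps its power. It serves here only as a yardstick, and was not stated for anti-Xa.
- A reader might also infer that the anti-Xa cut throws away most of the exposure information. A median split keeps about 64%; the share falls just below half only at about 20/80.
- Nor is anti-Xa the only usable exposure measure. Infusion rate is documented daily (section 5.5) and total duration is recorded (section 6.18), while anti-Xa is itself run by local laboratories (section 3).
- The 0.20 boundary is not arbitrary. It is the midpoint of the target range, and comparing the halves fits the stated preference for the upper end.
- These are three of thirteen subgroups in an 88-patient Phase II trial, and the raw values are collected whatever item 10 says.

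It can also be said that item 10 only names groups and that section 10.4 already provides multiple regression for prognostic factors. That does not dispose of the point. The protocol itself fixes these two-level designations, and a general provision for prognostic modelling does not say that the subgroup questions will be tested on the continuous values.

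**Conclusion.** The point holds as a modest one. Item 10 sets two-level forms for three measures that could be tested on their own scale. For a within-arm association as large as 0.37, that would cost about 18 points of power at a median split and more at an uneven one. The figure rests on a normal predictor and on borrowing 0.37 as the effect size. For Hijdra and hsCRP the proportional loss of information carries over, but no power figure can be drawn from the documents. Using continuous terms would not rescue a modest interaction in a trial of this size. The primary comparison, the sample size and the section 10.2 correlations are untouched. This is a worthwhile improvement, not a flaw that threatens the trial's conclusions.

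**What to change.** Amend item 10 of section 1.2.2 as follows:

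- Subgroups ii and v: base the test on a treatment-by-covariate interaction, using the Hijdra score as a continuous term and log(hsCRP).
- Subgroup xi: base it on a regression of 90-day MoCA on continuous day-6 anti-Xa within the LDIVH arm.
- Label all three as exploratory.
- Keep the two-level tables for display.

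The cost is analysis wording only, since every value is already collected. The small downside is that a linear trend is assumed, which a plot or a quadratic term can check. Continuous hsCRP removes the undefined threshold but not differences between local laboratories.

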2. BACKGROUND

2.1 Rationale

Aneurysmal subarachnoid hemorrhage (aSAH) comprises 5–7% of all strokes of which 30% will die from the initial hemorrhage or re-hemorrhage. Unfortunately, aSAH survivors are at high risk for subsequent severe neurological and neurocognitive complications, collectively referred to as “delayed neurological deficits” (DNDs). There is growing recognition that inflammation, both local (neuroinflammation) and systemic, plays an important role in the pathogenesis of cerebral vasospasm (CV) and DNDs after aSAH. Cognitive dysfunction and memory deficits are observed following many inflammatory states, including infection, traumatic brain injury, normal aging, and Alzheimer’s disease. Similarly, cognitive dysfunction and memory deficits are very

common following aSAH, leading to life-altering psychosocial deficits in patients with otherwise “favorable” outcomes.

The vascular inflammatory response in the central nervous system following aSAH induced vascular injury is multifocal and complex and is implicated in the development of cerebral vasospasm, delayed cerebral ischemia, and cognitive dysfunction. Numerous inflammatory and non-inflammatory biomarkers have been proposed as outcome predictors in aSAH. Some of the strongest evidence relates to elevation of inflammatory biomarkers IL-6 and high sensitivity C-reactive protein (hs-CRP) predicting poor outcome following aSAH. Other biomarkers that may predict poor outcome in aSAH include (but not limited to): HMGB-1, S100 family proteins including MRP-8/14 complex, P-Selectin, ICAM-1, TNF- α , MMP-9, and ICAM-1. Therapies designed to mute the severity of neuroinflammation following aSAH are prime candidates for investigation as they may allow an opportunity to prevent the development of DNDs including commonly occurring and often disabling cognitive dysfunction. In addition to the potential for direct neural injury from inflammation, inflammation can cause secondary effects such as fever. Fever has been associated with worse outcomes in many diseases of cerebral injury including aSAH exclusive of whether there is a concomitant infection. Modulation of the inflammatory response that has the secondary effect to reduce fever burden may also prove to be beneficial to aSAH patients.

Unfractionated heparin (UFH) is clinically utilized almost exclusively for its anticoagulant properties, yet heparin binding can interrupt numerous other biological pathways. Among its wide-ranging effects, heparin complexes with free hemoglobin itself, including oxyhemoglobin, blocks the activity of free radicals (FR) including reactive oxygen species (ROS), antagonizes endothelin-mediated vasoconstriction, binds several cytokines and all chemokines, thereby imparting potent anti-inflammatory effects. It is hypothesized that heparin may exert a therapeutic benefit in SAH patients by acting via one or more of these well-established anti-inflammatory mechanisms.

Recently, experiments utilizing a rat model of SAH, found that continuous intravenous administration of unfractionated heparin was able to downregulate neuroinflammation and prevent neurodegeneration, demyelination, and transynaptic apoptosis.

2.2 Supporting Data in Humans

Recent retrospective human aSAH studies evaluating the Maryland low-dose IV heparin (LDIVH) protocol provide evidence that heparin may reduce the incidence of symptomatic vasospasm requiring rescue therapy, vasospasm related CT infarction, and cognitive dysfunction. In [name] et al. (J Neurosurg 119:1611-1619) an analysis of 86 Fisher grade 3 aSAH patients treated with craniotomy and clipping was performed. The patients were enrolled concurrently and 43 LDIVH patients were compared to 43 control patients. The incidence of clinical vasospasm in the control group was 47%, and 9% in the LDIVH group ($p=0.0002$). When evaluating for CT evidence of vasospasm related infarction, there was a 21% incidence of CT infarct in the control group, and 0% incidence of CT infarct in the LDIVH treated group ($p=0.003$).

There were no hemorrhagic complications. Unpublished study data ([name]) presented during a symposium at the 2015 AHA/ASA International Stroke Conference demonstrated a significantly better ($p=0.013$) mean MoCA score of 26.4 in the LDIVH treated group ($n=25$) compared to 22.7 in the control group ($n=22$). [MoCA score range 0-30, normal 26-30]. A 3-point difference in mean MoCA scores is considered clinically relevant. The influence of heparin on MoCA remained significant after controlling for potential confounding factors with multivariate regression analysis. Additional preliminary data demonstrate that the Maryland LDIVH protocol can also mute elevations of the inflammatory biomarker myeloperoxidase (MPO) at 48 hours ([name], unpublished data). MPO has been previously identified to be elevated in serum after aSAH and at even higher levels in those patients with cerebral vasospasm. The Maryland LDIVH protocol has been administered to over 200 patients without any serious adverse safety concerns.

3. STUDY DESIGN AND OVERVIEW

This study is a Phase II, multicenter, prospective, stratified randomization, open-label, blinded adjudication, clinical trial evaluating the feasibility of LDIVH treatment in aSAH. The study personnel at the Imaging Core Lab, Biomarker Lab, and all personnel involved in evaluation of neurological and cognitive outcomes during the 90-day follow-up visit will be blinded to treatment allocation.

Each site will designate a separate clinical research team member(s) who will perform the the 90-day and 1-year follow-up visit clinical research assessments with subjects. These team members must remain blinded and therefore are not allowed to be involved in the day-to-day research procedures of the study prior to the 90-day follow-up visit (cannot have been involved with study subjects during the acute hospitalization period). This will usually require most study sites to have two or more clinical research nurses / coordinators available.

In this trial, 88 modified-Fisher grade 3 and 4 (subset of mFisher 4) aSAH patients with clinical WFNS grade ≤ 2 who have had their ruptured anterior circulation or basilar apex cerebral aneurysm secured by endovascular coil embolization and who remain without a new focal neurological deficit, aphasia or other major complication from their procedure will be eligible for enrollment (See formal inclusion and exclusion criteria Sections 4.1 and 4.2). Enrolled subjects will undergo a stratified randomization procedure (1:1) to one of two treatment arms (LDIVH vs Control). The stratified aspect of the randomization will attempt to evenly distribute sex, and the presence of ruptured anterior communicating artery (ACoA) aneurysms among the treatment arms. This will increase the likelihood of an even distribution of patients with these baseline characteristics within both treatment groups. ACoA aneurysms are implicated in causing greater cognitive dysfunction than other aneurysm location types, likely due to their classic frontal bleed pattern. Only subjects aged 70 years or less are allowed for enrollment, as advanced age can confound cognitive testing.

All subjects will receive mechanical DVT prophylaxis with sequential compression devices and / or TED Stockings per the usual SOC at each site. Compliance with this prophylaxis will be documented. Control subjects should additionally receive chemical DVT prophylaxis (5000 units of heparin subcutaneously twice daily) which will be considered within the range of SOC for each clinical site. LDIVH subjects will not receive chemical DVT prophylaxis while actively receiving the study drug. All LDIVH subjects will receive chemical DVT prophylaxis following cessation of the study drug infusion until discharge or ambulatory per the usual SOC at each clinical site. Subjects will undergo DVT / PE screening / assessment per the usual SOC at their facility, although we recommend screening by weekly lower extremity venous duplex as aSAH patients have been reported to have deep venous thrombosis in up to 20% and this may serve as justification for modifying the local SOC. Other heparin drug(s) and heparin coated catheters and devices will not be utilized in this study except for treatment of an urgent or emergent medical condition requiring heparin (eg. DVT, PE, dissection) or as mentioned above, for chemical DVT prophylaxis.

All patients should be monitored for the development of heparin induced thrombocytopenia with daily CBCs (platelet counts) and per the guidelines of the American Society of Hematology:

https://www.google.com/url?sa=t&rct=j&q=&esrc=s&source=web&cd=4&ved=0CD0QFjADahUKEwjuqvWcil3HhAhWEJR4KHWNbCp4&url=http%3A%2F%2Fwww.hematology.org%2FClinicians%2FGuidelines-Quality%2FQuick-Ref%2F529.aspx&ei=rXK_Va6qNITLeOO2qfAJ&usq=AFQjCNF64VDAzo5VXjZEKiWau t2Xmep7iA&bvm=bv.99261572,d.dmo

Daily CBCs will be considered SOC for this study. Potential HIT cases will be evaluated per recommended protocols and SOC at each site based on the guidelines above. Any case (or suspected case) of type II heparin induced thrombocytopenia (Heparin Induced Thrombocytopenia and Thrombosis - HIT) will be treated by stopping the study drug infusion in LDIVH subjects and otherwise treated per the usual SOC at each clinical site. These events will be documented in the adverse event reporting system.

Routine clinical blood work will be drawn per each site's SOC.

hs-CRP (Blood and CSF), Anti-Xa levels, and study related aPTT values are to be analyzed by the clinical lab at each site but will be paid for by the study. The dose adjustments of the LDIVH patients will not be based on the Anti-Xa levels, these are for research data analysis purposes only. The LDIVH dose adjustments will be based solely on aPTT values.

Blood drawn for additional biomarker analysis will be processed to plasma at each site. Plasma and CSF obtained by study personnel will then be stored in properly marked tubes at -70° Celsius until at least 6 patients have all samples collected. This will be the first batch designated for shipment to the Biomarker Core Lab. The second batch shipped to the Biomarker Core Lab will include all remaining subjects for that clinical site. Specimen batches from each site will be shipped on dry ice to the Core Biomarker

Lab at the University of Louisville where it will again be stored at -70° Celsius until batch analysis is performed after all samples have been received.

Neurological and cognitive evaluations (example: MoCA) will be performed during the acute hospitalization at various time points by trained study personnel. These clinical assessments will commonly occur on the same day as the biomarker blood draw (See Schedule of Events). This correlation will allow an enhanced analysis of a potential clinical treatment effect for LDIVH in relation to inflammatory biomarker level changes over time providing both clinical and laboratory biomarkers of disease.

Cognitive testing with MoCA and other clinical outcome measures are to be performed at the 90-day follow-up visit by separate trained study personnel. These personnel will remain blinded to treatment allocation and will not have been previously directly involved with the study subjects. A final MoCA will be performed at a 1-year follow-up.

[figure not shown]
Study enrollment will occur over 24 months or until enrollment goals are met. Data for the clinical trial will be collected via an online, web accessible, HIPAA compliant, secure database (<https://neurosurgery-research.redcap.louisville.edu>; OR <https://astroh.redcap.louisville.edu>) through electronic case report forms (CRFs) [REDCap] during the patient's acute hospitalization for their aSAH as well as during a single 90-day (+/- 10 days) and 1-year study follow-up period following the date of enrollment. Should the REDCap system be non-operational then paper CRFs will be utilized by each site. In this event, a separate binder will be created for each study subject and will be stored in a locked office or cabinet to prevent any HIPAA violations. The study will be complete after all study subjects (i.e., those that have not expired, withdrawn consent to participate in the trial, or been lost to follow-up) have completed their 1-year follow-up visit.

